## Research Plan and Methodology

### Study Design

This study was a randomized control trial. The effects of the intervention were tests using a two-arm randommixed controlled trial, comparing PFR (Arm 1) to Resource and Referral (Arm 2). Assessments were completed at T1 (before randomization), immediately after the intervention (T2), and a 6-month follow-up.

### Participants

The *Moms and Babies Program/Programa para Mamás y Bebés* (MBP) research procedures were reviewed and approved by the University of Washington Institutional Review Board. Between November 2015 and June 2019, 252 mothers with their infants living in King County, Washington were enrolled in the study. The flow of participant recruitment, assignment, and completion of assessments is shown in Figure 1. Information on demographic and other baseline characteristics, including mental health concerns (PHQ-9 depression and GAD-7 anxiety, Spitzer et al., 1999; PCL-C-SF post-traumatic stress disorder, Lang & Stein, 2005) is shown by condition in Table 1.

**Eligibility and recruitment.** Participants were eligible if they had received mental health treatment during pregnancy at one of the participating health centers, were conversant in English or Spanish, had an infant under three months of age, had access to a telephone, were planning to remain in the study area until the child's first birthday, and had not already received PFR. All aspects of the study, including the intervention and research visits, were offered in English and Spanish.

Study recruitment was conducted in collaboration with the Mental Health Integration Program (MHIP) and Maternity Support Services (MSS) of Public Health Seattle and King County, Washington. MHIP is based on a public health approach that uses a collaborative care model to treat behavioral health problems like depression, anxiety, and trauma symptoms through primary care clinics in low-resourced settings. Public Health in Seattle/King County (PHSKC) targets pregnant and parenting women for collaborative care through the MHIP Moms program. Five community health clinics offering MHIP agreed to assist in study recruitment. In addition to MHIP Moms, PHSKC offers MSS, provided by public health social workers, nurses, and nutritionists who deliver case management plus referral to community mental health services from pregnancy through two months postpartum. Mothers were recruited for the study through both mechanisms.

Eligible mothers were identified via the Mental Health Integrated Tracking System (MHITS), the data base for MHIP managed by PHSKC in King County, or the PHSKC MSS database. Each MHIP participating community health center 'owns' the list of its patients and agreed for the county public health department to generate a monthly list of eligible pregnant women receiving mental health services at each clinic. The monthly list contained the names of their own eligible patients who were pregnant or had an infant less than three months of age. MHIP care managers and MSS social workers talked with women on the list by phone or at a clinic visit, briefly outlining the study. If the mother spoke, English or Spanish and interested in learning more about the study, the care manager or social worker connected her to the study recruitment coordinator either immediately or through a follow-up phone call. The recruitment coordinator conducted additional screening and answered any questions the mother had. If the mother was eligible and interested, the study research visitor scheduled and conducted the first research visit when the baby was between 6 and 12 weeks old. Written informed consent was obtained at the first research visit.

The project director initiated the randomization after the first research visit was completed. Randomization into the PFR intervention or control condition was computer generated, blocked on language group. Sample attrition was very low. Follow-up research visits were conducted when infants were 6 and 12 months old. At both follow-up timepoints, over 94% of families in both conditions completed the assessments. Overall, 95.2% completed all three research visits, 2.0% completed only the first visit, 1.6% completed the first and second visits, and 1.2% completed the first and third visits. Comparing the 240 cases with complete data with the 12 cases that missed one or both follow-up timepoints, attrition did not differ significantly by condition, nor did tests of condition-by-baseline characteristics reveal any evidence of differential attrition by condition with respect to language, race/ethnicity, age of mother, baseline mental health measures, or any of the primary outcome measures. At baseline, mothers with incomplete data were more likely to be separated, divorced or widowed, had lower incomes, and had more children.

### ***Promoting First Relationship® (PFR) Intervention***

The manualized PFR intervention was delivered by seven female master's-prepared mental health professionals. Six were employees of a community agency, and one was employed by the University of Washington. Four primary providers, who were all employed by a community agency, worked with 93% of the study families, and three fill-in providers administered the intervention to the remaining 7%. Three of the providers were fluent in Spanish, and all were fluent in English. The providers completed PFR training and were certified before meeting with study families. Throughout the study, fidelity was monitored by a PFR master trainer. The providers were required to submit videotapes of themselves working with the families during the sixth session for each family on their caseload, which the master trainer reviewed to rate the quality of delivery. If a provider did not meet fidelity (i.e., received a rating of less than 4 on a 5-point scale), she received additional one-on-one mentoring from the master trainer until her fidelity to PFR was reestablished. Of 98 fidelity videotapes that were coded, 6% did not meet fidelity. Providers were not assigned additional families to work with until they reestablished fidelity. The PFR training model includes weekly reflective practice group sessions, facilitated by a PFR consultant, to support providers in their work with vulnerable families.

The majority of the 127 mothers randomized to PFR received a full dose of the intervention: 82% received 9-10 weekly sessions, 9% had 5-8 sessions, 8% had 1-4 sessions, and 2% did not start the intervention. The sessions typically ranged from 60 to 75 minutes and took place in the families' homes. The providers delivered activities and instructional content as prescribed in the PFR manual; however, the pace of delivery of these components was tailored to individual mothers, and some sessions were adapted for very young infants. A key component of PFR is videotaped caregiver-child interaction, completed during five sessions and serving as the focus of reflective video feedback during alternating weeks. The tapes were viewed together by the mother and intervention provider, who guided discussion focusing on parenting strengths and interpretation of her baby's cues.

### **Control Condition**

The 125 mothers randomized to the control condition were mailed a resource packet containing a listing of a variety of local resources, child development handouts, and parenting handouts. Packets were provided in the mother's desired language. The materials did not overlap with the content of PFR. To help minimize attrition, mothers in the control condition also

received two check-in phone calls before the second research visit to see if their contact information had changed and to answer any questions about the study.

## **Measures and Procedures**

Infants and their mothers were assessed in three 90-minute in-home research visits: at baseline (infant age 6-12 weeks), and when the babies were 6 months and 12 months old. The intervention was completed between the baseline and 6-month research visits. Assessments were conducted by three bilingual study research visitors who had bachelor's or master's degrees, who were blinded to intervention assignment, and whose offices were not near the intervention staff. One primary research visitor completed 96% of the research visits. The time from baseline to the 6-month research visit averaged 4.4 months, and the time from the 6-month to 12-month research visit averaged 6.0 months. Time between visits did not differ by intervention group. The research visits included standardized interview questions and videotaped mother-infant interactions. The consent form and all study measures were read to the participants to ensure understanding and minimize missing data. All measures have been used with mothers from different cultural backgrounds, including Latina mothers, in other studies. Research visits were conducted by telephone if the family moved outside of the study area after the first research visit (15 research visits), and also for the final five families completing the 12-month research visit due to stay-at-home requirements caused by the COVID-19 pandemic. Research visits were conducted in-person and in-home for 98% of the assessments. Study participants received \$50 in cash or gift card after each research visit to compensate for their time.

### ***Primary Caregiver Outcomes***

*Parenting sensitivity* was an observational measure collected at each research visit using the Nursing Child Assessment Teaching Scale (NCATS; Barnard, 1994). Mothers were presented with a list of activities and instructed to select the first activity that their infant could not yet do (e.g., hold onto a rattle, transfer an object from one hand to another, play pat-a-cake), to attempt to teach their infant. A standard set of manipulatives were provided for the activities. Teaching interactions were videotaped. Videotapes were scored by a blinded coder on 50 caregiver items measuring sensitivity to cues, response to distress, and fostering of social, emotional, cognitive growth, and contingency between caregiver and child. Items were scored yes (1) or no (0) and summed for a total sensitivity score. A single bilingual and bicultural coder, blind to intervention condition, was trained to reliability by a certified NCATS instructor and passed biannual reliability checks with a minimum of 85% inter-rater agreement with a master trainer.

The Infant CARE-Index (ICI, [name], 1979-2010) assesses parent-infant interaction during play and was included at each research visit. The mother was asked to play with her child as she usually would, and the interaction was filmed for 3-5 minutes. If mothers wanted to use toys, they were offered toys that they could use, or they could choose their own toys. The videos were scored by 16 coders certified to code the ICI for research purposes. To be certified, coders rated videos from a collection of videos gathered in multiple countries and that represented the full range of potential scores on the ICI constructs. Coders had to meet a standard for inter-rater reliability of  $r = .80$  on the measure of dyadic synchrony and an average of  $r = .70$  across all scales. Prior to coding the full sample in this study, coders coded 20 MBP study tapes, coder agreement was somewhat lower in this selection of videos ( $r = .74$ , range = .66 to .87). The coders' work was overseen by the author of the coding scheme ([name]). To address the study's primary hypotheses regarding caregiver outcomes, the rating for *dyadic synchrony* in play was used in the current study. Dyadic synchrony is any mutual pattern of behavior that

enables the infant to explore the activity with interest and spontaneity and without inhibiting or exaggerating negative affect. Dyadic synchrony scores of 11-14 are sensitive, with mutual delight or a smooth, pleasing interaction. Scores between 7 and 10 are adequate, with satisfactory play but noticeable periods of desynchrony. Scores between 5 and 6 reflect clear, unresolved problems and limited playfulness, but no evidence of hostility or unresponsiveness. Scores between 0 and 4 reflect high risk, with a clear lack of empathy, insufficient or unsuccessful attempt to respond to the infant, or total failure to perceive or attempt to soothe the infant, and no play. As a further check of reliability, approximately 20% of the videos were randomly selected to be coded by a reliability coder. Inter-rater correlations for dyadic synchrony between the two coders averaged  $r = .67$ .

*Understanding of infant and toddler behavior* was measured by the Raising a Baby Scale (RAB; Kelly, Korfomacher, & Buehlman, 2008). The RAB is a measure of caregiver knowledge of infant and toddler social-emotional needs and developmentally appropriate expectations. At each research visit, mothers rated the 16 RAB items on a 4-point scale (*strongly agree* to *strongly disagree*;  $\alpha$  ranged from .68 to .71 across the three time points). The scale was summed, and higher scores indicate greater parental knowledge.

*Maternal confidence*, the perceptions mothers have of their ability to care for and understand their infants, was measured at each research visit using the *Maternal Confidence Questionnaire (MCQ)* (Zahr, 1991). Mothers rated 14 items on a 5-point scale (*never* to *always*;  $\alpha$  ranged from .66 to .76 across the three time points). Maternal confidence is reflected by the mean of the scale, with higher scores indicating greater confidence.

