### **Secondary Infant Outcomes**

The Infant CARE-Index (described above) also yields scores for the infant's contribution to the interaction. We included *infant difficultness*. Scores could range from 0 to 14. Higher scores reflect more infant difficult behaviors, such as crying and fussing, turning away, negative facial expressions, avoidance of eye contact, high arousal, and lack of engagement in a developmentally satisfying shared activity. Inter-rater correlations for difficultness on the 20% of videos selected for coding by an additional coder averaged  $r = .49$ .

At the final research visit, when infants were 12 months old, infant *externalizing* behavior, *internalizing* behavior, and *dysregulation* were measured with mother's report on the *Infant Toddler Social Emotional Assessment (ITSEA)* (Carter & Briggs-Gowan, 2006). The ITSEA was not included at the baseline or 6-month research visits because it is not valid for children younger than 12 months. The ITSEA has been standardized and normed on a nationally representative sample that was stratified to match the 2002 United States Census. Mothers rated their infant on an extensive list of behaviors from 0 (*not true/rarely*) to 2 (*very true/often*). T-scores were calculated for externalizing, internalizing, and dysregulation domains. In the study sample, alpha reliabilities for the domains were  $\alpha = .81$  for externalizing,  $\alpha = .68$  for internalizing, and  $\alpha = .80$  for dysregulation.

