Cover Page
Statistical Analysis Plan

Official title of the study: Collaborative Perinatal Mental Health and Parenting Support in Primary Care

NCT Number: 02724774

Date of document: October 20, 2021 (created for ClinicalTrials.gov)

Analysis Plan

All analyses were conducted as intention-to-treat, analyzing all 252 cases as randomly assigned to the PFR and control group (CG). Multiple linear regression was used to examine the treatment effect of PFR (0 = CG, 1 = PFR) on study outcomes including the primary caregiver outcomes (parenting sensitivity, dyadic synchrony, understanding of infant and toddler behavior, and maternal confidence) and the secondary infant outcomes (infant difficultness, internalizing behavior, externalizing behavior, and dysregulation). Covariates included preferred language (0 = English, 1 = Spanish) and the baseline measure (unavailable for the ITSEA scales). Covariates were decided upon prior to analyzing outcome data to align with stratification in the randomization design (Moher et al., 2021) and obtain precise and unbiased estimates of the intervention effect (Van Breukelen, 2006). Adjusting for the baseline measure, which was expected to be the strongest correlate of outcomes, increases the precisions of intervention effect estimates. Standardized effect sizes (d) were calculated based on the unstandardized effect coefficient for PFR divided by the pooled standard deviation of the measure at baseline (if available) or at the follow-up time point (when the baseline measure was not available). The sign of the standardized effect was coded so that a positive d would reflect a desired positive effect of PFR on the given outcome (e.g., a positive d would reflect higher parent sensitivity or reduced externalizing behavior associated with PFR). We interpret ds as small (0.20), medium (0.50), and large (0.80; Cohen, 1988).

Regression analyses were conducted in Mplus Version 7.31 (Muthén & Muthén, 1998-2015). Covariate missingness was modeled to allow for inclusion of all 252 cases in all regression models, including cases with partially missing data (Muthén, et al., 2016; Muthén & Muthén, 1998-2015). Maximum likelihood parameter estimates with conventional standard

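### Does the protocol's silence on blinding of the 16 Infant CARE-Index coders call for a change to the analysis of dyadic synchrony and infant difficultness?

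*Protocol*

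**What the plan says.** Blinding is stated for two groups.

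- **Research visitors** (Protocol, Measures and Procedures): three visitors "who were blinded to intervention assignment, and whose offices were not near the intervention staff".
- **NCATS coder** (Protocol, Primary Caregiver Outcomes), twice: "Videotapes were scored by a blinded coder on 50 caregiver items", and "A single bilingual and bicultural coder, blind to intervention condition, was trained to reliability by a certified NCATS instructor".

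For the ICI, the same section says "The videos were scored by 16 coders certified to code the ICI for research purposes". It then describes quality control: a certification threshold ("Coders had to meet a standard for inter-rater reliability of" .80 for dyadic synchrony), 20 study tapes coded beforehand (r = .74), oversight by the author of the scheme, and double coding: "As a further check of reliability, approximately 20% of the videos were randomly selected to be coded by a reliability coder". The resulting correlation averaged .67 for synchrony. For the infant score, in Secondary Infant Outcomes, "Inter-rater correlations for difficultness on the 20% of videos selected for coding by an additional coder averaged" .49. Neither section mentions blinding of the ICI coders or the reliability coder, or the rule for allocating videos.

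The SAP's Analysis Plan does not mention blinding. Its regression model has no coder term: "Covariates included preferred language (0 = English, 1 = Spanish) and the baseline measure (unavailable for the ITSEA scales").

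**The concern.** The contrast lies within one section: the NCATS paragraph states blinding twice, and the ICI paragraph that follows it does not state it at all. A reader may infer that the ICI coders were not blind.

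The stakes would be real. Two of the four primary outcomes are mothers' reports, from women who know whether they had home sessions or a mailed packet. The two observed outcomes are where blind assessment can help, and it is documented for only one. Synchrony is a rater's judgement about the quality of an interaction. Baseline videos precede randomization, so a lean toward PFR that arose only at follow-up would pass undiminished into the PFR coefficient.

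The reliability figures do not answer the question. Agreement between coders shows whether they rank dyads alike, not whether they share a tilt by arm.

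**Working it through.** The documents give no figure for coder bias, alpha or power, so there is nothing of the plan's own to reproduce. What follows shows what a lean would do, and whether the data could reveal one.

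**Inputs from the documents.** Of 252 families, 95.2% (240) completed all three visits, 1.6% (4) the first and second, and 1.2% (3) the first and third. So 240 + 4 = 244 were seen at 6 months and 240 + 3 = 243 at 12 months. Visits total 252 + 244 + 243 = 739, of which 487 are follow-ups. About 20% were double-coded: 148 overall, 97 at follow-up. Inter-rater r is .67 (synchrony) and .49 (difficultness).

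**Assumptions.** A lean L toward PFR of 0 to 0.30 SD, a two-sided 5% test, equal arms, and a baseline–outcome correlation rho of 0 or 0.5.

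**1. Lean at follow-up only.** SE = sqrt((4/N)(1 − rho²)). With N = 244 this is 0.128 at rho = 0 and 0.111 at rho = 0.5. The rejection rate under no true effect (noncentral t, noncentrality L/SE) is:

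| L (SD) | rho = 0 | rho = 0.5 |
|---|---|---|
| 0 | 5% | 5% |
| 0.10 | 12% | 15% |
| 0.20 | 34% | 44% |
| 0.30 | 65% | 77% |

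**2. The same difference at baseline and follow-up.** This could arise if each dyad's videos went to the same coder and coders were divided by arm. Adjusting for baseline then leaves L(1 − rho). At rho = 0.5 the residual is 0.05, 0.10 and 0.15 SD for L = 0.10, 0.20 and 0.30. The rejection rates are about 7%, 15% and 27%, against 15%, 44% and 77% in the table. The documents do not say when coding was done or how it was allocated, so they cannot tell these cases apart.

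**3. Does the inter-rater correlation reveal a lean?** If both coders lean, r becomes (r + L²/4)/(1 + L²/4). If only the first leans, it becomes r/sqrt(1 + L²/4). At L = 0.30 (L²/4 = 0.0225), .67 moves to .677 or .663. The Fisher-z 95% interval for .67 on 148 videos is .57 to .75, treating the averaged r as one correlation on independent videos. The correlation is uninformative about a lean in either direction.

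**4. Would an added check reveal it?** Take the first-minus-second rating difference by arm on 97 double-coded follow-up videos, with a blind second coder and equal rater error. The SD of the difference is sqrt(2(1 − r)): 0.812 for synchrony and 1.010 for difficultness. SE = 2 × SD/sqrt(97) = 0.165 and 0.205, and the 95% half-widths are 1.96 × SE = 0.32 and 0.40 SD. Power at L = 0.30 is about 44% and 31%; at L = 0.20, about 23% and 16%.

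Measures and Procedures reports 15 telephone visits and five more families assessed by telephone at 12 months. If 20 visits gave no play video (assumed), 467 follow-up videos remain, about 93 were double-coded, and the half-widths become 0.33 and 0.41 SD.

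**5. Would a coder term help?** It corrects for severe and lenient coders being spread unevenly across arms. It does not correct for a coder scoring one arm more kindly. It also needs coder identities, which the documents do not say were kept.

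**The case for a change.** The strongest case for acting is that the omission is genuine, concerns a primary outcome, and cannot be resolved from the documents. Blinded visitors do not settle it, since they conducted the visits while other people scored the ICI tapes. The authors themselves reported visitor and NCATS coder blinding as separate facts. Certification and agreement do not settle it either, as step 3 shows. A sentence costs almost nothing, and without it a reader cannot call synchrony assessor-blind.

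All of that stands as a remark on reporting. It does not make the case for changing the analysis. A net lean of 0.30 SD requires 16 coders to know the arm and tilt the same way on average, or an allocation that followed arm; no passage points to either. The filming was done by people blind to arm, and nothing indicates that tapes carried arm labels. The table in step 1 would look the same for any outcome given a bias of that size, so it is no evidence about this one. The gap between .67 in the study and the .80 certification standard also has no bearing on blinding; certification used videos chosen to span the full range of scores.

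**Conclusion.** No change to the plan. The protocol leaves unsaid whether the ICI coders and the reliability coder were blind and how videos reached them. This is missing description of the study's conduct, not a faulty rule. The regression on arm, language and baseline is the right primary analysis if the coders were blind, and no passage suggests that they were not. The SAP is a retrospective document, dated October 2021 and prepared for the registry, so the silence may be no more than uneven drafting. The trial team can supply the fact wherever the results are reported.

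The size of any bias is unknown. The false-positive rates of 12% to 77% rest wholly on an assumed lean of 0.10 to 0.30 SD confined to follow-up, an assumed 5% test and an assumed rho. If the same difference is present at baseline and rho is 0.5, they fall to about 7% to 27%. The double-coding comparison would add little, since its half-widths of 0.32 and 0.40 SD exceed the whole assumed range, and it needs a second coder known to be blind. A coder-adjusted estimate addresses uneven allocation only. Until the fact is stated, a reader should treat the two ICI outcomes as not documented to be assessor-blind, which is different from shown to be biased.

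### Does scoring of the Infant CARE-Index by 16 coders mean the treatment model needs a coder term?

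*Protocol*

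**What the plan says.** Under Primary Caregiver Outcomes, the Protocol says that the ICI "assesses parent-infant interaction during play and was included at each research visit", so the baseline covariate is coder-scored as well as the outcome. On the scoring it says: "The videos were scored by 16 coders certified to code the ICI for research purposes". The teaching scale (NCATS) was handled differently: "A single bilingual and bicultural coder, blind to intervention condition, was trained to reliability by a certified NCATS instructor".

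Several controls on ICI coding are described:
- Coders had to meet a certification standard.
- A check was made on study material: "Prior to coding the full sample in this study, coders coded 20 MBP study tapes", with agreement of r = .74.
- The work was "overseen by the author of the coding scheme".
- On double-coding: "approximately 20% of the videos were randomly selected to be coded by a reliability coder".

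For the primary ICI outcome, "Inter-rater correlations for dyadic synchrony between the two coders averaged" r = .67. Under Secondary Infant Outcomes, "Inter-rater correlations for difficultness on the 20% of videos selected for coding by an additional coder averaged" r = .49.

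Neither document says how videos were assigned to their primary coder. The SAP's Analysis Plan fits a linear regression on arm, preferred language and the baseline measure, with conventional maximum likelihood standard errors. It has no coder term.

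**The concern.** With 16 people scoring one scale, some will mark higher than others. If those differences are stable, scores from the same coder are correlated, and a model that ignores coder treats them as independent. Two things could go wrong:

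- **Precision.** Severity differences inflate the residual variance, so the treatment estimate is noisier than it need be.
- **Validity.** If some coders scored mostly one arm, severity differences would add to the between-arm difference, the standard error would be too small, and the test would reject too often.

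The reported correlations do not settle the matter. Within a fixed pair of coders, r does not register a constant shift between them. Pooled over pairs, it registers the shift only in part. The text says only that the correlations averaged these values. One of the four primary outcomes is affected, so the question deserves a check.

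**Working it through.** **Inputs.** The documents give arms of 127 and 125 (127 + 125 = 252), 16 coders, and r = .67 and .49. They give no coder variance or allocation figure, so there is no plan figure to reproduce.

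**Scored videos per follow-up.** From Eligibility and recruitment, 240 families completed all visits, 1.6% of 252 = 4 completed only the first two, and 1.2% = 3 completed only the first and third. That gives 244 visits at 6 months and 243 at 12 months, 487 in all. Removing 15 + 5 = 20 telephone visits (assumed to have no video) leaves 467, about 234 per follow-up, split roughly 118/116. Per coder, 234/16 is about 15.

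**Assumed severity share, ρ.** Take 0 to 16.5% for synchrony and 0 to 25.5% for difficultness. These are half of 1 − r: (1 − .67)/2 and (1 − .49)/2. This is a rough guide and not an estimate. Strictly, 1 − r refers to score variance; after baseline adjustment with an assumed slope of 0.4, 16.5% of score variance is about 16.5/0.84 = 20% of residual variance. If r was computed within pairs, it sets no ceiling at all.

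**Validity.** Let p₁c and p₀c be coder c's share of the videos in each arm. The true variance of the arm contrast, relative to what the planned model assumes, is

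ratio = (1 − ρ) + ρ · Σ(p₁c − p₀c)² / (1/n₁ + 1/n₀),

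and the type I error is 2[1 − Φ(1.96/√ratio)].

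- *Allocation independent of arm, even workload.* The expected sum divided by (1/n₁ + 1/n₀) is 1 − 1/16 = 0.9375, so ratio = 1 − 0.0625ρ. At ρ = 25.5% this is 0.984. Type I error is 4.8 to 5.0% over the whole range.
- *Allocation balanced by arm.* The sum is zero and ratio = 1 − ρ, so the planned standard error is conservative.
- *Systematic lean.* Suppose half the coders lean to each arm, with chance variation on top. Here 1/118 + 1/116 = 0.0171. For 60/40 the systematic part is 16 × 0.025² = 0.010 and the chance part is 0.935, giving 0.010/0.0171 + 0.935 = 1.52. For 70/30 it is 16 × 0.05² = 0.040 and 0.9275, giving 3.27.

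| ρ | Independent of arm | 60/40 lean | 70/30 lean |
|---|---|---|---|
| 10% | 5.0% | 5.6% | 7.7% |
| 16.5% | 4.9% | 6.0% | 9.5% |
| 25.5% | 4.8% | 6.6% | 11.9% |

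Simulation of the planned regression gave the same pattern.

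**Is a lean plausible?** Randomization was by computer and blocked on language, and language is a covariate. Assigning Spanish videos to Spanish-speaking coders would therefore not separate the arms. Both arms were recruited concurrently and seen at the same infant ages, so assignment by date or by visit would not separate them either.

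**Precision.** In simulations with allocation independent of arm, the SD of the treatment estimate with a follow-up-coder random intercept, divided by the SD without it, was as follows (even / uneven workload):

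| ρ | SD ratio |
|---|---|
| 0 | 1.001 / 1.001 |
| 5% | .995 / .987 |
| 10% | .970 / .973 |
| 16.5% | .956 / .935 |
| 25.5% | .897 / .894 |

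If the same coder scored a family at baseline and follow-up, the baseline covariate already carries the coder's severity. The ratio is then .986 to 1.000 for ρ of 5 to 25.5%. A further random intercept for the baseline coder moves the ratio by at most .001 up to ρ = 16.5%.

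**What a coder-by-arm table could show.** With 15 videos per coder and assignment unrelated to arm, the expected majority share is 0.5 + E|X − 7.5|/15. Since E|X − 7.5| = 15 × 3432/32768 = 1.57, this is 0.605. An average coder would show about 60/40 by chance alone.

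**The case for a change.** The best case for acting is that the harmlessness of omitting coder rests on one unreported fact: how each coder's videos divide between arms. A 16-row table would show it without any model, and an absolute-agreement coefficient could be computed from videos already double-coded. Blinding is stated for the NCATS coder but not for the ICI coders, so the text does not exclude an allocation that followed arm. At a 70/30 lean the planned test would run at roughly 8 to 12% for shares of 10 to 25.5%, and in simulation a coder random intercept brings it back to 5.4 to 5.8%.

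Much of this is correct as arithmetic, and fuller reporting would help a reader. It does not show a fault in the plan. The 70/30 case is hypothetical, and the severity share is assumed. The table is a weak diagnostic at this size, because chance splits of about 60/40 could be mistaken for a lean. If ICI coders knew the arm and scored accordingly, the estimate would be biased in a way that a coder intercept cannot repair, so the blinding point does not argue for that term. The model also needs coder identifiers, which the documents do not say were kept.

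**Conclusion.** No change to the plan. The factual basis is right: 16 coders, no stated allocation rule, no coder term. With allocation independent of arm, the planned test holds its level (4.8 to 5.0% by formula). The cost of ignoring coder is then precision alone: for synchrony, nil to about 6.5% of the SD of the treatment estimate at shares up to 16.5%; for difficultness, nil to about 10% at shares up to 25.5%. It is close to nil if one coder scored both visits.

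This rests on two things. The severity share is an assumption, since the reported correlations do not identify it. Independence of allocation from arm is inferred from the randomized design and the absence of any contrary statement; it is not documented. The SAP fixed its covariates before outcome data were analyzed, so a coder term would be a post hoc addition beside an unchanged primary estimate. Videos per coder by arm, the basis of r, an absolute-agreement coefficient and the blinding of ICI coders are details that a report may usefully supply. Their absence does not make the planned analysis wrong.
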